#### Background

Postoperative urinary retention (POUR) is a significant postoperative complication in 14-16% of all surgeries (Kowalik) and 21-50% following female pelvic reconstructive surgery (Ripperda). POUR is associated with increased risk of urinary tract infection and healthcare costs (Hooten) as well as decreased patient satisfaction (Kenton).

The bladder neck and urethra are rich in  $\alpha$ -adrenergic receptors. One potential mechanism by which POUR occurs following female pelvic reconstructive surgery is disruption of the local autonomic nervous system, increasing sympathetic drive to the bladder outlet and inhibiting urethral relaxation and bladder emptying. The prophylactic use of  $\alpha$ -AR antagonists before the onset of symptoms may decrease the incidence of POUR after urologic and colorectal surgery in men (Ghuman, Akkoc, Poylin, Claney). Recently, a retrospective matched cohort study by Chapman et al. showed a significantly decrease risk of POUR with the use of tamsulosin following female pelvic reconstructive surgery. In this study, active voiding trials were performed on postoperative day 1 for the tamsulosin group. In a follow-up double-blinded randomized controlled trial, a 10-day course of tamsulosin started 3 days preoperatively vs. placebo showed a reduction in POUR from 24.6% in the placebo group to 8.7% in the tamsulosin group (Chapman). The voiding trials in this study were performed on postoperative day 1.

With enhanced recovery after surgery protocols, same-day discharge has become a common phenomenon with female pelvic reconstructive surgery. It is safe and cost effective for patients with no increase in postoperative complications as compared to an overnight stay (Schiavone, Jennings, Carter-Brooks). Same day hospital discharge with voiding trials performed on the day of procedure, however, may be associated with even higher rates of acute POUR. In our unit, at least 50% of women undergoing multicompartment native tissue vaginal repair, who are discharged on the same day, have to perform either self-catheterization or have an indwelling Foley catheter which increases patient burden and risk of UTIs. It may also decrease overall patient satisfaction.

The purpose of this double-blind, randomized controlled trial is to determine the difference in incidence of POUR following a postoperative day 0 voiding trial in patients undergoing multicompartment native tissue vaginal repair of pelvic organ prolapse, with or without concomitant mid-urethral sling, who received 0.4 mg of tamsulosin 5 days pre- and post-operatively compared to those who receive placebo. The 5-day period was determined based on the pharmacokinetics of tamsulosin. Given the recent trend in

same-day discharge, increasing the success of postoperative day 0 voiding trial would theoretically decrease the percentage of patients going home with indwelling Foley catheters, increase patient satisfaction and decrease urinary tract infection rates. Additionally, continuing tamsulosin for 5 days postoperatively to prevent decrease in steady-state blood levels may theoretically reduce the incidence of delayed urinary retention.

# Specific Aims

# Primary Aim(s):

(1) To compare rates of POUR following an active voiding trial on postoperative day 0 between women undergoing multicompartment, native tissue vaginal repair that received perioperative tamsulosin versus women that received placebo

# Secondary Aim(s):

- To compare the mean total number of days of postoperative catheterization, incidence of delayed urinary retention and urinary tract infection rates up to 6 weeks post-surgery between groups
- (2) To compare ED visits and serious adverse events, as classified by Clavien-Dindo, between groups
- (3) To compare patient level of satisfaction with voiding function immediately prior to hospital discharge and at 1 week post-procedure.

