#### Secondary:

To compare the following between the two groups:

- 1. Postoperative urinary tract infection rates (up to 6 weeks post-surgery)
- Incidence of delayed urinary retention (defined as PVR > 150 ml up to 6 weeks post-surgery)
- 3. ED visits and serious adverse events within 30 days post procedure
- 4. Total number of days of catheterization
- 5. Patient level of satisfaction with voiding/bladder function immediately prior to hospital discharge: Very dissatisfied, moderately dissatisfied, slightly dissatisfied, neutral, slightly satisfied, moderately satisfied, very satisfied

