# **Reporting Adverse Events:**

In a study by Kaplan, AE's in women and children were abdominal pain, asthenia, constipation, dizziness, dry mouth, drowsiness, dyspepsia, headache, incontinence, nasal congestion, nausea, orthostatic hypotension, and somnolence.

The overall safety profile in women seemed to be generally consistent with the profile in men.

Patients will initially be screened for these adverse events on postoperative day 1 via telephone call.

Adverse events (AEs) will be recorded and reported to local IRB as per regulations on Serious Adverse Event reporting guideline. Post-operative and surgical attributed AEs will be defined using the Clavien-DINDO grading

TABLE 1. Classification of Surgical Complications Clavien-DINDO Grade Definition for surgery attributed post-op events only

Grade 1	Any deviation from the normal postoperative course without the need for pharmacologic treatment. Allowed therapeutic interventions are: drugs as antiemetics, antipyretics, analgesics, physiotherapy
Grade II	Requiring pharmacological treatment with drugs other than such allowed for grade I complications Blood transfusions and total parenteral nutrition are also included
Grade III	Requiring surgical, endoscopic or radiological intervention Intervention not under general anesthesia
IIIA IIIB	Intervention under general anesthesia
Grade IV	Life-threatening complication (including CNS complications)* requiring IC/ICU management
IVA	Single organ dysfunction (including dialysis)
IVB	Multi-organ dysfunction
Grade V	Death

Protocol Specific Reportable AEs include those determined to be related to postoperative recovery as listed below:

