#### Medication-related:

Orthostatic hypotension/dizziness Postoperative atrial fibrillation Abdominal pain Asthenia Constipation Dry mouth Drowsiness Dyspepsia Headache Nasal congestion Nausea Somnolence

Underlying diseases are not reportable as AEs unless there is an increase of severity or frequency during the course of the study. If an AE has not resolved at the time of AE Form completion, save form as incomplete in REDCap until resolved. Once resolved, update AE form, and enter into REDCap and save form as complete.

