# Adverse Event Definitions:

Adverse Event: any untoward medical occurrence, unintended disease or injury, or any untoward clinical signs (including abnormal laboratory finding) in subjects, whether or not related to the administration of IP versus placebo.

Serious Adverse Event: an adverse event that Led to death

Led to serious deterioration in the health of the subject that either resulted in

- a life-threatening illness or injury
- a permanent impairment of a body structure or a body function in subject or prolonged hospitalization of existing hospitalization
- medical or surgical intervention to prevent life-threatening illness or injury or permanent impairment to a body structure or a body function

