#### Relationship of AE to Operative Procedures:

Unrelated: No evidence that the timing if the AE has a relationship to the administration of study drug.

Possibly Related: The AE has a timely relationship to the study drug, however a potential alternative etiology may be responsible for the AE.

Probably Related: The AE has a timely relationship to the study drug and the causative relationship can clearly be established. No potential alternative etiology is apparent.

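### Aim 2 and Outcome 3 give the between-arm SAE comparison different scopes, and non-serious drug events and the preoperative dosing days fall in no stated comparison

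*Combined protocol and SAP*

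**What the plan says.** The scope of the safety comparison has to be pieced together from several sections of the combined protocol and SAP.

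- **Secondary Aim(s), item 2** is the only safety aim: "To compare ED visits and serious adverse events, as classified by Clavien-Dindo, between groups". It states no time window.
- **Outcomes, Secondary, item 3** lists the comparison as "ED visits and serious adverse events within 30 days post procedure". It mentions neither Clavien-Dindo nor attribution.
- **Reporting Adverse Events** introduces the grading with "Post-operative and surgical attributed AEs will be defined using the Clavien-DINDO grading". The caption of Table 1 is narrower: "Grade Definition for surgery attributed post-op events only".
- **Adverse Event Definitions** counts an adverse event "whether or not related to the administration of IP versus placebo". It defines a serious event by its consequence, with no reference to a Clavien-Dindo grade.
- **Medication-related** lists the expected drug events, beginning "Orthostatic hypotension/dizziness Postoperative atrial fibrillation Abdominal pain Asthenia". There are 12 entries, all reportable and entered in REDCap.
- **Study Intervention** starts dosing 5 days before the day of surgery, for 10 days in total.
- **Power analysis** names general tests for numerical and categorical data and does not mention adverse events.

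**The concern.** The randomised factor is tamsulosin; every woman has surgery. A safety comparison between arms should therefore be able to show harm from the drug. Aim 2, read with the Table 1 caption, uses a scale that has no place for a drug-attributed event, while Outcome 3 has no such limit. An analyst following the plan could defend either set of events, and could choose after seeing the data.

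Prophylaxis also gives the drug to every treated woman in order to spare some of them a catheter. Tolerability is therefore part of the benefit-risk question, and most of it lies in non-serious events such as dizziness. The plan anticipates and records those events but does not say that they will be compared. Its only stated safety window opens at surgery, after half of the dosing days have passed.

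**Working it through.** The main check is a reading of the sections against each other. The table follows five kinds of event through the two statements of the comparison.

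| Event | Aim 2 | Outcome 3 |
|---|---|---|
| Serious, surgery-attributed, within 30 days post procedure | Included | Included |
| Serious, drug-attributed, within 30 days post procedure | Unclear: Table 1 gives it no grade | Included |
| ED visit for any cause, within 30 days post procedure | Included | Included |
| Listed medication-related event, non-serious, no ED visit | Not included | Not included |
| Any event in the preoperative dosing days | An SAE has no grade, because the scale is for post-operative events; no window stated | Not included |

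The second row is the inconsistency. The fourth and fifth rows are the gaps.

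*Listed drug events.* The 12 entries are orthostatic hypotension/dizziness, postoperative atrial fibrillation, abdominal pain, asthenia, constipation, dry mouth, drowsiness, dyspepsia, headache, nasal congestion, nausea and somnolence. None is named in the primary or secondary aims or outcomes. Each reaches Outcome 3 only if it is serious or leads to an ED visit in the window.

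*Exposure outside the window.* Dosing runs for 10 days from 5 days before surgery, so 5/10 = 50% of the dosing days come before the day of surgery. Outcome 3 counts only from the procedure.

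*Women who leave early.* Randomization is at the preoperative clinic visit. Exclusion 1 removes women with certain intraoperative complications after randomization and drops them from the per-protocol analysis. Their preoperative doses were due by then. No safety population is stated, so the plan does not say whether their events count.

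*What a comparison could show.* The planned enrolment is 44 per arm (37 before the dropout allowance).

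- With no SAE in an arm, the one-sided 95% upper limit for its true rate is 1 − 0.05^(1/n). This is 6.6% for n = 44 and 7.8% for n = 37. A comparison of SAEs alone will therefore say little about tolerability.
- For a listed drug event, the half-width of the 95% interval for the risk difference is 1.96 × √[(p₁(1−p₁) + p₂(1−p₂))/44]. The documents give no event rates, so the rates here are assumed over a range.
  - At 5% versus 10%: 1.96 × √[(0.0475 + 0.09)/44] = 1.96 × 0.0559 = 11.0 percentage points.
  - At 10% versus 30%: 1.96 × √[(0.09 + 0.21)/44] = 1.96 × 0.0826 = 16.2 percentage points.
- Power at 44 per arm (two-sided 5% level) is about 14% for 5% versus 10% and 66% for 10% versus 30%.

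Intervals this wide support a descriptive table and do not support formal tests.

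**The case against.** A reader of Aim 2 and the Table 1 caption might infer that the trial compares no drug-related harm at all. The documents do not support that. Outcome 3 carries no attribution limit, and the definitions behind it cover any cause. A drug-caused SAE within 30 days after surgery is therefore compared. ED visits are not limited by cause even in Aim 2, so a faint that led to an ED visit would count.

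The wording of Aim 2 can also be defended. To classify events is to grade them, and nothing says that an ungraded SAE is dropped. The sentence that introduces the grading can be read more widely than the caption. Aim 2 has no window, so a preoperative ED visit could be argued into it. These points weaken any claim of a deliberate filter. They do not remove the ambiguity, because the caption says *only* and the one stated window starts at the procedure.

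A reader might also infer that the plan gives no means of deciding what is surgery-attributed. That goes too far. The separate lists of surgery- or catheter-related and medication-related events give a rough split, and attribution is made blind, so no bias towards an arm is shown. The section headed "Relationship of AE to Operative Procedures" has categories that describe the relation to study drug. This looks like a labelling slip and should be corrected.

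Finally, the non-serious drug events are missing from Aim 2 because it concerns serious events, and not because of Clavien-Dindo. Rewording the SAE comparison would not bring them in. They are recorded, and a routine by-arm table could show them. That is fair, and it is why the remedy is cheap. It is still better to name the table, its population and its window in advance.

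**Conclusion.** The point holds as an inconsistency and two gaps. Aim 2, Outcome 3, Table 1 and the adverse event definitions do not agree on whether the SAE comparison is limited to surgery-attributed events, and they must be reconciled. Medication-related events that are non-serious and lead to no ED visit are in no stated between-arm comparison. Nor are events in the preoperative dosing days, taking Outcome 3's window as the operative one.

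The size is 12 of 12 listed drug entries named in no aim or outcome, and 5 of 10 dosing days outside the only stated safety window. How many women this affects cannot be derived, because the documents give no event rates. The conclusion rests on taking the Table 1 caption at its word and on the general tests in the Power analysis section not amounting to a planned adverse event comparison.

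This should be changed, but it does not threaten the primary result. It affects neither the sample size nor the primary analysis.

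**What to change.** 1. In Aim 2 and Outcome 3, use one wording: SAEs as defined under Adverse Event Definitions, whatever the cause, and ED visits, compared between arms from first dose to 30 days post procedure.
2. State that Clavien-Dindo is used only to describe surgical complications and does not decide which SAEs are compared.
3. Add one by-arm table giving the number of women with each of the 12 listed medication-related events. Include all who took at least one dose, with those who exit under exclusion 1. Give risk differences with 95% confidence intervals and label the table descriptive.
4. Correct the heading of the relatedness section so that it matches its categories.

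The cost is wording in two sections and one extra table of events already reportable. The intervals will be wide at about 44 per arm, so the absence of a visible difference must not be read as evidence of safety. The bottle log tracks bottles out and in, and no pill count is described, so a data field confirming the first dose may be needed. The first stated adverse event screen is the telephone call on postoperative day 1. Preoperative events may therefore be under-captured, and a footnote to the table should say so.

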# Hypothesis

Peri-operative administration of tamsulosin decreases the incidence of POUR on postoperative day 0 in female patients who undergo multicompartment native tissue vaginal repair compared to those who receive placebo.

Keywords: ERAS (enhanced recovery after surgery) POUR (postoperative urinary retention) FPRS (female pelvic reconstructive surgery) IP (investigational product) FPMRS (female pelvic medicine and reconstructive surgery)

# Study Design

This is a double-blind, randomized controlled trial. Both investigators and participants will remain blinded to the intervention. All surgery will be performed by FPMRS board-certified urogynecologists. The patients will be able to have a revealing of the intervention they received at 6 weeks post-surgery

# Outcomes

#### Primary

To compare rates of POUR following an active voiding trial on postoperative day O between women undergoing multi-compartment native tissue vaginal repair that received preoperative tamsulosin 5 days preoperatively and continued 5 days post operatively versus a group that received placebo

#### Secondary:

To compare the following between the two groups:

- 1. Postoperative urinary tract infection rates (up to 6 weeks post-surgery)
- Incidence of delayed urinary retention (defined as PVR > 150 ml up to 6 weeks post-surgery)
- 3. ED visits and serious adverse events within 30 days post procedure
- 4. Total number of days of catheterization
- 5. Patient level of satisfaction with voiding/bladder function immediately prior to hospital discharge: Very dissatisfied, moderately dissatisfied, slightly dissatisfied, neutral, slightly satisfied, moderately satisfied, very satisfied

#### Inclusion criteria:

- 1. Stage II or greater pelvic organ prolapse in > 1 vaginal compartment
- 2. Plan for multicompartment native tissue vaginal repair (which would include any combination of uterosacral ligament suspension, sacrospinous ligament suspension, cystocele and/or rectocele repair, with or without hysterectomy and with or without concomitant mid-urethral sling) or vaginal closure with FPMRS-trained surgeons at Wake Forest Baptist Health.
- 3. Participation in Enhanced-Recovery-After-Surgery protocol with plan for sameday hospital discharge
- 4. Willing to remain compliant with IP.

# Exclusion criteria:

- 1. Intraoperative complication necessitating prolonged bladder drainage or placement of a vaginal pack x 24 hours (patients would exit study after randomization and will be excluded from the per-protocol analysis)
- 2. Patients whose surgical plan would necessitate a voiding trial on postop day >0
- 3. Less than 21 years of age
- 4. Unable to understand English
- 5. Patients who are scheduled to undergo combined colorectal procedures such as rectopexy, sphincteroplasty
- 6. Patient with known allergy to tamsulosin or sulfa drugs
- 7. Patients with upcoming cataract surgery
- 8. Patient with orthostatic hypotension
- 9. History of postvoid residual (PVR>150) prior to surgery with prolapse reduction
- 10. Patients with hypertension on alpha-blockers
- 11. Single compartment prolapse repair (anterior or posterior repair only)
- 12. Use of mesh for prolapse repair
- 13. High tone pelvic floor dysfunction

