# Randomization -

All enrolled and consented patients will undergo randomization at their pre-operative clinic visit. A study patient can be randomized into either tamsulosin IP or Placebo IP group. Randomization assignment will occur through sealedenvelope.com-generated random allocation using a randomly permutated block design (8 subjects per block). An

unblended designated person who will not participate in data collection or analysis will be responsible for providing randomization schedule. Study staff will dispense the assigned IP bottle (see below) in the urology clinic. Study patient charts will get updated with the IP ID (e.g. 01A, 02A, 01B, 02B...). Research staff administering follow-up questionnaires will also be blinded to the subject's randomization. The subject will be asked to bring back their IP bottle at the time of their postoperative visit.

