#### Study Intervention –

10 pills of each IP and placebo will be placed in identical coded containers and stored in a locked area in the clinic. Instructions for IP usage will be provided to subjects for 10 days of usage as 0.4 mg qd by PO route starting 5 days prior to day of surgery and continued for a total 10 days. The research manager will be the only member of the study team who has the research key designating which containers are IP versus placebo.

On postoperative day 0 after recovery from anesthesia, each patient will have their bladder emptied using the indwelling Foley and their bladder will then be retrograde-filled with 300 cc of normal saline and given 30 minutes to void. A postvoid residual volume<150 cc will be considered a success of the voiding trial. If the voiding trial was considered failed, the patient will have a foley catheter reinserted and the patient will be instructed to remove the catheter at home after having a bowel movement. If they are unable to void at home within 4 hours of catheter removal, they will return to the Wake Forest Urology clinic for self-catheter teaching.

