#### Post-Surgery Assessments -

Postoperative day 0 voiding trial result For women who fail initial trial of void, post-operative day when bladder function returned Postoperative exam at 1 and 6 weeks Pelvic examination at 6 weeks Data points to be collected: Post-void residual (PVR), urinalysis (UA), patient level of satisfaction (1-7 – very dissatisfied, moderately dissatisfied, slightly dissatisfied, neutral, slightly satisfied, moderately satisfied, very satisfied)

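### Randomized, treated women who have a qualifying intraoperative event leave the study, and no as-randomized analysis set or continued follow-up is described for them

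*Combined protocol and SAP*

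**What the plan says.** **Timing.** The Randomization section says: "All enrolled and consented patients will undergo randomization at their pre-operative clinic visit". The Study Intervention section schedules the product "starting 5 days prior to day of surgery and continued for a total 10 days". A woman on schedule therefore reaches the operating room already randomized and exposed.

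**Exit.** Exclusion criteria, item 1, covers an intraoperative complication that requires prolonged bladder drainage, or a vaginal pack kept for 24 hours. Of these women it says "patients would exit study after randomization and will be excluded from the per-protocol analysis".

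**Outcomes.** The primary outcome is "To compare rates of POUR following an active voiding trial on postoperative day" 0. The secondary outcomes include urinary tract infection to 6 weeks, total catheter days, and "ED visits and serious adverse events within 30 days post procedure".

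**Follow-up.** Post-Surgery Assessments plans a "Postoperative exam at 1 and 6 weeks". Reporting Adverse Events says: "Patients will initially be screened for these adverse events on postoperative day 1 via telephone call". An adverse event is defined as "any untoward medical occurrence, unintended disease or injury", whether or not related to the product. Neither adverse-event section makes an exception for women who exit.

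**Analysis.** The Power analysis section allows 20% for non-compliance and dropout (44 enrolled per arm) and lists the tests. It attaches no analysis population to them and does not say whether non-compliant women are analysed.

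**The concern.** An eligibility criterion is normally settled before allocation. This one is settled at surgery, so it works as a removal after randomization. Leaving out randomized women because of something that happened later gives up part of the protection that randomization provides.

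Two things are at stake.

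- **Secondary and safety comparisons.** If exit ends data collection, the infection, catheter-day and emergency-visit and serious-event comparisons lose women who had a surgical complication or a 24-hour pack. Those who exit for prolonged drainage would contribute catheter days directly.
- **Primary comparison.** No as-randomized set is defined and no set is called primary. The plan therefore does not fix how women who exited, or who did not take the product, enter the main result.

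**Working it through.** **Step 1: passages side by side.** Randomization comes at the pre-operative visit, product starts 5 days before surgery, the exit event occurs during surgery, and the voiding trial follows on day 0. Exit therefore falls after allocation and scheduled exposure but before the primary outcome. The exit wording suggests that follow-up stops; the adverse-event text and the 30-day readmission and reoperation items in Appendix A exempt nobody. The document does not settle which governs.

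**Step 2: reproduce the plan's sample size.** Inputs from Power analysis: control 0.243, tamsulosin 0.029, 5% significance (two-sided assumed, since sidedness is not stated), 80% power.

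n per arm = (1.960 + 0.842)² × [0.243 × 0.757 + 0.029 × 0.971] / (0.243 − 0.029)² = 7.849 × 0.2121 / 0.0458 = 36.35, rounded up to 37. This matches the plan.

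**Step 3: power at 44 per arm, same formula.** Power = Φ(difference / √(variance sum / n) − 1.960). With no loss: 0.214 / √(0.2121/44) = 3.08, and Φ(3.08 − 1.96) = 86.9%.

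**Step 4: cost of analysing as randomized when some women take no product.** Assume a share c of tamsulosin women took none and had the control rate. The tamsulosin rate becomes (1 − c) × 0.029 + c × 0.243. The last column leaves the same share out of both arms, so n = 44 × (1 − c).

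| c (assumed) | Tamsulosin rate | Power, as randomized | Power, left out |
|---|---|---|---|
| 5% | 0.0397 | 81.6% | 85.2% |
| 10% | 0.0504 | 75.6% | 83.2% |
| 20% | 0.0718 | 62.1% | 78.7% |

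**Step 5: women with no day-0 trial.** Assume an event rate q, equal in both arms. Counted as not passing, the rates are q + (1 − q) × 0.243 and q + (1 − q) × 0.029 with n = 44. Left out, the rates stay as planned and n = 44 × (1 − q).

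| q (assumed) | Rates if counted | Power, counted as not passing | Power, left out |
|---|---|---|---|
| 2% | 0.258 vs 0.048 | 81.4% | 86.2% |
| 5% | 0.281 vs 0.078 | 73.2% | 85.2% |
| 10% | 0.319 vs 0.126 | 60.8% | 83.3% (n = 39.6) |

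Counting these women as not passing adds equal failures to both arms and costs far more power than leaving them out. It suits a sensitivity analysis better than a primary rule.

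**The case against.** - **The handling is partly stated.** For intraoperative exits the plan says in advance that they leave the per-protocol analysis, and the 20% allowance also points toward leaving women out. This stands. What is missing is narrower: which set is primary, whether follow-up continues, and how other women without a day-0 trial (for example after cancelled surgery) are handled.
- **Naming a per-protocol analysis implies another one.** It may, and the plan never calls per-protocol primary. But an implied set is not a defined one.
- **The trial is blinded.** Study Design keeps investigators and participants blinded, so exit should not depend on knowledge of the arm. This stands. A reader might infer that the rule biases the primary result, but the documents do not support that: they show a risk only and give no event rate.
- **A reader might also infer that the missing rule could decide significance.** That requires counting women with no trial as failures, which no passage suggests and which assigns a failure a woman may not have had.
- **The power levels depend on the method and on no other losses.** Enumerating the chi-square test itself gives 90.5% at 44 per arm, not 86.9%. The gap between rules is similar: about 89%, 88% or 86% left out against 84%, 74% or 61% counted. The tables also treat non-compliance and exit one at a time.

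**Conclusion.** The point holds as an inexpensive improvement. Randomized women scheduled for five days of product exit for an intraoperative event. Read literally, the rule removes them from three secondary or safety comparisons and leaves per-protocol as the only described basis for the primary one. It does not show that the primary analysis is per-protocol, that follow-up will in fact stop, or that the result is biased.

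The size of any bias is unknown. The power figures rest on the plan's rates of 24.3% and 2.9%, the formula that reproduces its 37 per arm, and assumed non-compliance and event rates. The finding covers the supplied text only: front pages were removed, and the Abstract listed in the index is not in it.

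**What to change.** These changes concern follow-up and analysis only, not treatment.

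1. **Follow-up.** Replace study exit with continued follow-up through the existing 1- and 6-week visits. Include these women, in the arm assigned, in the infection, catheter-day, and emergency-visit and serious-adverse-event comparisons.
2. **Analysis set.** State that the primary comparison analyses women in the arm assigned regardless of pills taken, with per-protocol as supportive.
3. **No day-0 trial.** Report these women by arm with reasons, including cancelled surgery. Before unblinding, specify one sensitivity analysis that counts them as not passing.

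**Cost.** Protocol wording, one sensitivity analysis and one table; no new visits. Catheter days caused by a surgical complication will add noise to that comparison, by an amount the documents do not allow to be sized. Keeping non-compliant women costs the power shown in Step 4, so adherence should be reported by arm.

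**Separate item.** Outcomes (Secondary) defines delayed retention by residual volume up to 6 weeks, while Appendix A restricts it to women who passed a first trial. These passages need reconciling in their own right.
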